4.3 Participant Registration

[figure not shown]
Study registration will occur after the informed consent process is completed, consent form is signed and screening eligibility is confirmed. No study procedures will be conducted until after the consent form is signed, either electronically or a paper copy mailed or faxed to the clinic. To be enrolled in this study following screening, the participant must meet each criterion listed on the eligibility checklist based on the eligibility assessment documented in the case report record. Upon completion of the screening evaluation, and confirmation of eligibility, the study coordinator or designee will enroll the subject into REDCap.

5 Experimental Design:

Smokers will undergo a screening and then a three phase, 9 week experimental trial (Figure 1) with a one month follow-up at Week 10:

- 1) Phase 1 – Usual Brand Baseline: 1 week baseline assessment period of usual brand cigarette smoking;
- 2) Phase 2 – Study Cigarette Adaptation & Baseline Period: 2 week period allows the subject to adjust to the ventilated study cigarettes and obtain baseline data prior to randomization;
- 3) Phase 3 – Intervention: Randomization to either ventilated or unventilated study cigarettes for 6 weeks.

Figure 1:

[figure not shown]

Design

Subjects will be randomized at the end of Phase 2 (Visit 00) to one of the two experimental conditions (ventilated vs. unventilated cigarettes) for the 6-week intervention. An intervention

of six weeks was chosen because compensation is likely to stabilize by two weeks and biomarker levels should stabilize by six weeks.^{12,13}

Figure 2. Intervention Groups

Subjects will be informed of their assignment to ventilated cigarettes (cigarettes with similar ventilation as their usual brand) or unventilated cigarettes. As described above, study cigarettes are provided under single-blind conditions where subjects will not be informed of the filter design of the study cigarettes.

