6.2 Biological Specimens

Biological samples will be collected and brought to the clinic or curbside visits for biomarkers analysis. Subjects will be asked to collect urine and saliva sample at weeks 92, 00, 3 and 6 visits for biomarker assessments. Buccal cells will be collected during the telehealth, in-person clinic visit or curbside at weeks 0 and 6. Blood spots (optional) will be collected at weeks 00 and 6. Hair collection will be optional and collected at week 6. These optional samples will be used to determine the feasibility of collection and analytic capabilities and concordance of results across biosample type. Participants who have experienced extensive hair loss will be exempt from the hair sample collection. The optional biosamples collected over the duration of the study will be at the discretion of the lead PI's. This would occur if it is determined that one type of biomarker has a negative impact on recruitment (e.g., few people willing to collect hair sample) or we find the sample(s) collected do not yield sufficient biomarker levels. Cigarette butts (24-hour collection) will be collected at visits 00, 3 and 6 and the butts from the inhalation measures.

Samples will be stored in a -20 or -80°C freezer. Specimens will be collected, stored at sites and shipped to the Masonic Cancer Center at intervals upon request from the lead site.

The samples may be stored until they are used up or no longer needed up to a maximum of 10 years from the study's end. A subject has the right to withdraw consent at any time by informing the Principal Investigator by following the instructions provided in the HIPAA document. If this occurs any remaining identifiable research sample(s) will be destroyed.

Rationale for choice of biomarkers:

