To determine the sample size for a test of non-inferiority for unventilated filter cigarettes compared to ventilated filter cigarettes (control group), we used pilot data from our original ventilated/unventilated study 1 ([name], personal communication). For the purposes of sample size considerations, we will focus on total NNAL as one of the primary outcomes. Seventy subjects had a baseline NNAL value while smoking their usual brand and 19 and 16 subjects had an end of study NNAL value for the ventilated and unventilated groups, respectively. The endpoint of interest is the change in NNAL from baseline. To normalize the distribution of NNAL, the calculations were performed in the log scale. The non-inferiority margin (NIM) was set at a 15% change between groups. This criterion was chosen because it is close to, but not greater than the upper limit of the 95% confidence interval (CI) for the geometric mean of the change in NNAL. Therefore, 73 subjects per group will achieve 80% power to detect non-inferiority for the mean change in NNAL using a one-sided, two sample t-test with a significance level of 0.05. Furthermore, with these sample sizes, a one-sided, two-sample t-test for the mean difference in cigarettes per day (CPD) from baseline will have 90% power to determine non-inferiority with a significance level of 0.05 if the NIM is 2 cigarettes. A mean difference between ventilation groups of less than 2 cigarettes is considered to be in the range of equivalence. To accommodate a 10% loss-to-follow-up rate, we plan to enroll 81 subjects per group for a total of 162.

Study Populations

Intent-to-treat

The first analysis of all primary and secondary endpoints will adhere to the intent-to-treat principle. Under this principle, all subjects randomized to one of the two study arms will be included in the analysis in the group to which they were randomized regardless of protocol violations and compliance to treatment assignment.

Per-Protocol

A second per-protocol analysis will include only participants who complete the 6 week visit without protocol violations or non-compliance.

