The above methods will be supplemented with multiple linear regression analysis to include the baseline (visit 00) value for NNAL or CPD and the stratification variable (site), plus any other subject specific characteristics which might not be balanced between the study groups (p-value<0.2).

Finally, NNAL and CPD will be analyzed for all visits, starting at visit 00, using a linear mixed effects model (SAS PROC MIXED). The fixed effects are ventilation group indicator, plus other potential predictors. To model the variation within subjects, several candidate variance-covariance structures will be compared using both graphical and information criteria. Variance parameters will be estimated using restricted maximum likelihood method with the Satterthwaite approximation. This analysis will provide useful information about the change in toxicant exposure and the change in the number of cigarettes smoked per day over time.

Both linear regression models and repeated measures analysis can be modified for the equivalence and non-inferiority testing situations.³⁴

Secondary Endpoint Analysis

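### Usual-brand NNAL (visit 92) and Phase 1 cigarettes per day are measured before randomisation but named as covariates in no model, so a cheap precision gain on the primary tests is not secured

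*Combined protocol and SAP*

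**What the plan says.** **Collection.** Section 6.2 (Biological Specimens) states: "Subjects will be asked to collect urine and saliva sample at weeks 92, 00, 3 and 6 visits". Section 5.14 lists the visit 92 urine among the required samples, and the procedure table shows total NNAL at BL-92. Daily text reports of cigarettes start after the screening visit and run through Phase 1 (section 5.4). Randomisation takes place at visit 00 (section 5), so the usual-brand values precede it.

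**Analysis (section 10.2).** The two primary endpoints are described as Week 6 values adjusted for their visit 00 (Phase 2) counterparts. The stated primary analysis is nevertheless a one-sided two-sample t-test on the increase from visit 00, with no covariates. The supplementary model is a "multiple linear regression analysis to include the baseline (visit 00) value for NNAL or CPD and the stratification variable (site"), plus subject characteristics that appear unbalanced at p<0.2. For the mixed model, "NNAL and CPD will be analyzed for all visits, starting at visit 00"; its fixed effects are group and unspecified potential predictors. The secondary biomarkers follow the NNAL approach, using visit 00 and Week 6.

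**Sample size (section 10.1).** "73 subjects per group will achieve 80% power to detect non-inferiority for the mean change in NNAL". The calculation assumes a one-sided t-test at level 0.05. "The non-inferiority margin (NIM) was set at a 15% change between groups". For CPD the same numbers are said to give "90% power to determine non-inferiority with a significance level of 0.05 if the NIM is 2 cigarettes".

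**The concern.** Each randomised participant should have two pre-randomisation NNAL values and two pre-randomisation periods of cigarette counts. The plan names only the later of each. If repeat log NNAL values correlate highly, replacing a change score by adjustment for a single baseline gains little, because one urine sample carries about as much noise as the outcome. A second baseline value may then remove more of that noise.

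At stake is the width of the confidence bound that decides NNAL non-inferiority, which is planned at only 80% power against a 15% margin. A covariate measured before randomisation can be adjusted for without introducing bias, and the samples are already scheduled.

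**Working it through.** **Inputs from the documents:** 73 per group, one-sided alpha 0.05, 80% power for NNAL with a 15% margin on the log scale; 90% power for CPD with a margin of 2 cigarettes. **Not in the documents, so assumed:** a true difference of zero; the margin read as ln(1.15) = 0.1398; a between-subject SD, s, of log NNAL from 0.6 to 1.0, equal at all visits; and all correlations.

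**Step 1. The plan's own figure.** No SD is given, so 73 cannot be reproduced, only inverted. With the noncentral t on 144 degrees of freedom, 80% power requires a change SD of 0.338. Check by the normal formula: 2 × 0.338² × (1.645 + 0.842)² / 0.1398² ≈ 72.3, which rounds up to 73. For CPD, 90% power implies a change SD of 4.11 cigarettes per day.

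**Step 2. Implied correlation of visit 00 with Week 6.** The change variance is 2s²(1 − r), so r = 1 − 0.338²/(2s²). This gives 0.841, 0.911 and 0.943 for s = 0.6, 0.8 and 1.0.

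**Step 3. Residual variance of the Week 6 value.** Let a = corr(visit 92, Week 6) and q = corr(visit 92, visit 00).
- Change score: 2s²(1 − r)
- ANCOVA on visit 00: s²(1 − r²)
- ANCOVA on visits 00 and 92: s²(1 − R²), with R² = (a² + r² − 2arq)/(1 − q²)

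If a = rq, visit 92 tells us nothing beyond visit 00, and the second and third variances are equal.

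**Step 4. NNAL power at 73 per group** (noncentral t, one degree of freedom deducted per baseline covariate; site ignored).

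| | s = 0.6 | s = 0.8 | s = 1.0 |
|---|---|---|---|
| Change score | 80.0% | 80.0% | 80.0% |
| Visit 00 as covariate | 82.8% | 81.6% | 81.0% |
| Both, visit 92 uninformative (a = rq) | 82.8% | 81.6% | 81.0% |
| Both, q = r, a = r − 0.05 | 85.5% | 82.7% | 81.0% |
| Both, all correlations equal (a = q = r) | 89.8% | 89.4% | 89.3% |

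Relative to visit 00 alone, residual variance falls by 21%, 23% and 24% in the last row, by 8%, 3% and 0.1% in the row above it, and by nothing in the row above that. Visit 92 therefore adds from 0 to about 8 points of power (at s = 1.0, 89.3 − 81.0 = 8.3).

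**Step 5. Cost when the covariate is useless.** Losing one degree of freedom from 144 moves power from 80.00% to 79.998%.

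**Step 6. Does the p<0.2 rule already secure the gain?** Under randomisation any one baseline variable crosses p<0.2 about one time in five, whatever its prognostic strength. The rule also applies only to the supplementary regression.

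**The case against.** **Routes by which these values could enter.** A reader might infer that the usual-brand values are shut out of every model and the precision simply discarded. The documents do not say that. The regression admits characteristics unbalanced at p<0.2, the mixed model allows other predictors, and the imputation models use unspecified baseline covariates. What stands is narrower: neither value is prespecified, and the available routes are data-driven and outside the deciding test.

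**Size.** The gain rests on correlations that the documents do not give. Power near 90% needs visit 92 to predict Week 6 as well as visit 00 does, despite a longer interval and a change of product. Lowering both visit 92 correlations by 0.05 would still give 85.0-87.6%, but that treats visit 92 as no closer to visit 00, about two weeks later, than to Week 6, about eight weeks later. Holding q at r gives only 81.0-85.5%. The 0.338 is itself borrowed: the sizing paragraph describes a usual-brand pilot baseline, whereas the endpoint is change from visit 00.

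**Transition.** It is tempting to argue that visit 00 is still drifting from the usual brand, because section 5 says "compensation is likely to stabilize by two weeks and biomarker levels should stabilize by six weeks" and Phase 2 lasts two weeks. That sentence justifies the length of the intervention, and two weeks is the time it gives for compensation. Eligible brands were also chosen to approximate the ventilated study cigarette. Residual drift is possible but not established.

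**CPD.** The single-noisy-urine argument does not carry over. The CPD baseline is already a mean over Phase 2, and planned power is 90%. No gain is claimed for CPD beyond the general principle.

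**Conclusion.** The point holds as one of efficiency. Visit 92 NNAL and Phase 1 mean CPD are pre-randomisation measurements that no model prespecifies, and the deciding tests use no covariates at all. For NNAL, on the stated assumptions, moving from the change score to ANCOVA on visit 00 raises power from 80% to 81-83%. Adding visit 92 takes it to somewhere between about 81% (no added information) and about 90% (equal correlations). Where in that range the trial falls cannot be read from the documents. The CPD gain is not quantified.

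Nothing here implies bias or loss of type I error control in the planned tests. Nor would adding a covariate to the supplementary regression alone help, since the t-test would still decide the trial.

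One inconsistency bears on the choice of baseline. A footnote to the procedure table describes the Week 00 sample as a back-up baseline, whereas section 10.2 makes it the baseline for every primary comparison.

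**What to change.** - Replace the t-test as the primary NNAL analysis with a prespecified ANCOVA of Week 6 log NNAL on group, visit 00 log NNAL, visit 92 log NNAL and site. Keep the 15% margin and the one-sided 0.05 level. This also brings the test into line with section 10.2's own description of the endpoints as adjusted for visit 00.
- Use the same form for CPD, with Phase 2 mean and Phase 1 mean CPD as covariates and the 2-cigarette margin, and for TNE, CEMA and PheT, which keep their planned estimation with 95% intervals.
- Fill a missing visit 92 covariate with the mean of the observed pre-randomisation values pooled over both groups, so that nobody is dropped for it.
- Reconcile the Week 00 footnote in the procedure table with section 10.2.

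**Cost:** a rewritten primary-analysis paragraph and one corrected footnote, agreed before unblinded data are seen. The Phase 1 covariate takes one degree of freedom per model. No new visits, samples or assays are needed, because total NNAL is already scheduled at visit 92.

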10.2 Statistical analysis plan

The primary objective of the statistical analysis is to compare the effects of cigarette ventilation between two study groups: ventilated filter cigarettes and unventilated filter cigarettes. All statistical analyses will be performed using SAS version 9.4 (SAS Institute Inc., Cary NC) and a p-value less than 0.05 will be considered significant.

Describing the Study Population

Descriptive statistics will be performed for data collected on demographic characteristics, subjective measures and biomarkers at different phases and visits. Baseline data will be compared between the two ventilation groups with the two-sample t-test or the non-parametric Wilcoxon rank sum test for continuous or ordinal variables and chi-square tests for categorical variables. Biomarker data may be log transformed if necessary.

Primary Endpoint Analysis

The primary endpoints are (1) the total NNAL at the 6-week visit adjusted for NNAL at end of Phase 2 (visit 00); and (2) the mean CPD based on 7 days ITR data before week 6 visit adjusted for the mean CPD during Phase 2 (visit 00). The analysis of these two endpoints will evaluate non-inferiority of the unventilated group compared to the ventilated group.

Primary Analysis

The primary analysis will be a one-sided, two-sample t-test for non-inferiority. The null hypothesis for total NNAL (analyzed in the log scale) is that the increase from end of Phase 2 (visit 00) is 15% greater in the unventilated group compared to the ventilated group. The NNAL alternative hypothesis is that the increase from baseline (visit 00) is no higher than 15% in unventilated over ventilated groups. If the null hypothesis is rejected in favor of the alternative hypothesis, we will conclude that the unventilated filters are no more harmful in terms of NNAL exposure than the ventilated filter and may actually be less harmful. Similarly for the CPD, the non-inferiority t-test will have a null hypothesis that the 6 week mean increase in CPD from end of Phase 2 (visit 00) for the unventilated group is greater than 2.0 cigarettes compared to the ventilated group. The alternative hypothesis is that the CPD increase in the unventilated group is no more than a mean of 2.0 cigarettes verses the CPD increase in the ventilated group and the unventilated group may even smoke fewer cigarettes.

Secondary Analysis

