The secondary analyses include the other biomarkers (as listed above). The analysis for these potential toxicants will be the same as that outlined above for NNAL with measurements at end of Phase 2 (visit 00) and at the 6 week visit. A non-inferiority margin has not been established for many of these biochemical measures. Instead, group differences or ratios (if in the log scale) will be estimated with their 95% CI and examined as to whether or not they contain 0 for differences or 1 for ratios. Inhalation measures and smoking intensity (solanesol levels in the filter butts) will be analyzed with similar methods as the change in biomarker and CPD with regression models incorporating-covariates for baseline variables that may be different between groups ($p\text{-value}<0.2$). The FTND as a measure of dependency is a composite score that ranges from 0 to 10. With the expectation of non-inferiority for the unventilated group, a linear regression model for FTND at 6 weeks will include the FTND at baseline (visit 00) and the ventilation group indicator, plus any other important subject characteristic. The 95% CI for the estimated coefficient for the group indicator will be calculated to verify that it contains the value zero, indicating no difference in dependency between ventilation groups. The mCES and PHR questionnaires produce a series of subscales. To identify differences between ventilated and unventilated groups, non-parametric methods will be utilized, first with the Wilcoxon signed rank test to check for changes from end of Phase 2 to 6 weeks within each ventilation group and then with the Wilcoxon rank sum test for differences between groups.

Exploratory Analysis

The exploratory analysis for the other volatile organic biomarkers (listed in section 6.2) will be the same as that outlined above for NNAL and the other secondary biomarkers.

Correlation procedures (Pearson and Spearman) will measure the degree of association for the same biomarkers assayed from two or more biosamples.

Safety Endpoints

AEs and SAEs will be recorded as described in the Adverse Event SOP. AEs and SAEs will be tabulated separately for the two groups. We expect study product-related AEs and SAEs to be rare in this trial and, therefore, no formal statistical comparison of the rate of AEs and SAEs across treatment groups is planned for this trial.

Missing Data

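### Extra covariates in the supplementary and some secondary regressions are chosen by baseline imbalance at p<0.2, not by prognosis fixed in advance

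*Combined protocol and SAP*

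**What the plan says.** For NNAL and CPD, section 10.2 is explicit about the main test: "The primary analysis will be a one-sided, two-sample t-test for non-inferiority". Under Secondary Analysis it then says: "The above methods will be supplemented with multiple linear regression analysis". Two terms of that regression are fixed, since it is "to include the baseline (visit 00) value for NNAL or CPD and the stratification variable (site"). Further terms are then added: "plus any other subject specific characteristics which might not be balanced between the study groups (p-value<0.2").

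Under Secondary Endpoint Analysis, inhalation measures and smoking intensity get "regression models incorporating-covariates for baseline variables that may be different between groups", with the same 0.2 threshold. The other secondary biomarkers follow the NNAL methods. They have no margin and are read by whether a 95% interval contains 0 (differences) or 1 (ratios).

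The tests that would feed the rule are planned under Describing the Study Population: "Baseline data will be compared between the two ventilation groups with the two-sample t-test or the non-parametric Wilcoxon rank sum test", with chi-square tests for categorical variables. No candidate list is given. The covariates of the mixed model and of the FTND model are left open.

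**The concern.** Allocation is randomised in blocks and stratified by site (section 10.1). Any other baseline imbalance is therefore chance, and a balance test at 0.2 admits each candidate with probability 0.2 regardless of whether it predicts the outcome. A strong predictor that happens to be balanced is left out, and an irrelevant variable that happens to be imbalanced goes in. The model is known only after the arms have been compared, so two analysts with different candidate lists could report different adjusted results.

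At stake is the reliability and precision of the adjusted estimates that support the NNAL and CPD conclusions and that serve as the planned analysis for inhalation and intensity. For endpoints read by whether an interval contains no difference, lost precision is not neutral. The trial expects exposure to be no higher with unventilated filters, and a wide interval leans towards that answer. For intensity, where a difference is expected, it costs power.

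**Working it through.** **Inputs from the documents.** 73 per group, 80% power, one-sided 0.05, NNAL margin 15% on the log scale (section 10.1).

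**Reproducing 73.** The margin is ln(1.15) = 0.1398. The SD of log change is not stated. With true difference 0 it can be back-solved:

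SD = 0.1398 / [√(2/73) × (1.645 + 0.842)] = 0.1398 / (0.1655 × 2.487) = 0.340, or 0.338 with the noncentral t.

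An SD of 0.338-0.340 returns 73. Because it is solved from 73, this sets the scale for what follows and does not confirm the sample size.

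**How often the rule acts.** With k independent candidates, the expected number selected is 0.2k and the chance of at least one is 1 − 0.8^k.
- k = 8: 1.6 selected; 1 − 0.8^8 = 0.832.
- k = 15: 3.0 selected; 1 − 0.8^15 = 0.965.

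**Effect on the planned regression.** Simulation with the visit 00 value and site in every regression, 73 per group, SD of change 0.338, 20,000 trials at the margin (error) and 10,000 at no difference (power). Assumed, because the documents do not say: 8 or 15 independent candidates, three of them prognostic and known in advance, and a visit 00 to week 6 correlation of 0.5 or 0.8.

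| Correlation | Candidates | Residual variance explained | Error under rule | Power: visit 00 + site only | Power: rule | Power: pre-specified |
|---|---|---|---|---|---|---|
| 0.5 | 8 | 0% | 4.7% | 88.0% | 87.1% | - |
| 0.5 | 8 | 10% | 4.7% | 88.9% | 88.9% | 91.0% |
| 0.5 | 8 | 30% | 3.9% | 88.8% | 90.9% | 95.7% |
| 0.5 | 15 | 30% | 3.8% | 88.3% | 89.7% | 95.9% |
| 0.8 | 8 | 0% | 4.9% | 83.2% | 82.4% | - |
| 0.8 | 8 | 10% | 4.6% | 83.4% | 83.3% | 86.1% |
| 0.8 | 8 | 30% | 4.1% | 83.5% | 86.1% | 92.5% |

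- The unadjusted t-test has error 4.9-5.2% and power of about 80% throughout.
- Shortfall against pre-specification at 10%: 91.0 − 88.9 = 2.1 and 86.1 − 83.3 = 2.8 points.
- Shortfall at 30%: 95.7 − 90.9 = 4.8, 95.9 − 89.7 = 6.2 and 92.5 − 86.1 = 6.4 points.
- Runs at correlation 0.7 gave 83-87% under the rule against 88-94% pre-specified, hence the rounded ranges of 2-5 and 5-7 points. A further check at correlation 0.8 with 15 candidates and 30% explained (6,000 trials) gave 84.4% against 92.7%, just over 8 points.
- Monte Carlo error in the table is about 0.15 points for error and up to 0.4 points for power.

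**Why the error is conservative.** A predictor is left out when its imbalance is small, so it adds little to the spread of the estimate, yet its variance stays in the residual. At 30% explained with 8 candidates:
- mean model SE against actual spread is 0.0481 / 0.0448 = 1.07 (correlation 0.5) and 0.0526 / 0.0491 = 1.07 (correlation 0.8);
- pre-specified adjustment matches (0.0412 against 0.0414);
- the rule's interval is 0.0481 / 0.0412 = 1.17 times as wide as the pre-specified one.

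**Inhalation subset.** Its size is not stated. With non-prognostic extras at an assumed 20 per arm, the SE rises by about 4% (5 candidates), 7% (8) or 14% (15). At 40 per arm the range is about 2% to 7%.

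**The case against.** The strongest reply is that little of consequence depends on this rule, and much of that stands.

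- **The primary conclusion.** A reader might infer that the primary non-inferiority result is compromised. The documents do not support that. The primary test is a two-sample t-test with no covariate selection. Section 10.2 does describe the primary endpoints as adjusted for the visit 00 value, which sits awkwardly with that test and needs its own reconciliation, but it names the t-test as primary and the regression as a supplement.
- **False claims of non-inferiority.** A reader might infer that data-driven selection inflates them. In every setting run, error under the rule was at or below the nominal level, apart from simulation noise.
- **Prognostic variables displaced.** For NNAL and CPD the visit 00 value, probably the strongest predictor, and site are already fixed. Only the extras are at issue.
- **Power below the planned 80%.** With the visit 00 value and site in the model, the rule gives 82-91% in the table. Against those two terms alone it costs about 1-2 points if the extras are not prognostic, is about neutral at 10% explained, and gains a little at 30%. The shortfall is only against pre-specification, and that comparison assumes the right three covariates were named.
- **A large loss for inhalation.** That cannot be asserted without a subset size or a candidate list.

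What remains is that the rule selects on the wrong criterion and leaves the model open until the arms have been compared. A conservative error rate is also no comfort for endpoints where failing to exclude no difference is the favourable finding.

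**Conclusion.** The point holds for the supplementary NNAL and CPD regression, for the inhalation and intensity regressions, and for secondary biomarkers to the extent that they inherit the NNAL regression. It does not reach the primary t-test.

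The harm is a mild miscalibration in the safe direction and some forgone precision. It is negligible if the extra covariates are weak and moderate if they are strong. The figures rest on the assumed candidate count, prognostic strength and correlation, none of which the documents give, so the direction is firm and the size is indicative. The change is worth making because the remedy is easy and makes the adjusted analyses reproducible.

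**What to change.** In section 10.2, delete the p<0.2 rule under Secondary Analysis and under Secondary Endpoint Analysis. Before any outcome data are compared by arm, name a short covariate list to add to the visit 00 value of the outcome and site. That timing is used because the trial is single-blind and the plan describes no unblinding step. Choose the list for expected prognosis from data already collected; sex, menthol type and the visit 92 saliva nicotine metabolite ratio are examples. The documents do not show that these predict each outcome, so the team should justify its choice. Use the same list in these regressions and in place of the open covariate wording for the mixed model and for FTND.

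The cost is SAP wording only, with no new data or participants. The downside is that a pre-specified covariate that proves non-prognostic loses a little precision: for three such covariates, about 1% in SE at 73 per arm and about 4% at 20 per arm. The list for the inhalation subset should therefore be very short. Dropping p-values from the baseline table is optional reporting style.
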